7.6 Second Treatment Course

Any patient who failed prior treatment (i.e. met section 4.2.2 of the eligibility criteria at enrollment) will have a bone marrow biopsy and aspirate performed prior to the start of the 2nd treatment course.

A second treatment course will be given 6 to 8 weeks after the start of course 1, identical to the first course substituting the frozen NK cell product for the fresh product, unless medically unsafe.

The following criteria must be met before a new treatment course is started:

- ANC recovery to baseline documented prior to course 1
- Platelet transfusion that can be managed safely in the outpatient setting

- Treatment related non-hematologic toxicity, except fatigue, alopecia, resolved to \leq grade 2
- Absence of rapid disease progression as defined in Section 7.10

If the above requirements are not met, delay and reassess weekly until recovery occurs. If more than 2 weekly delays occur (>8 weeks from the start of course 1) without hematological recovery and/or non-hematologic treatment related toxicity resolution, the patient will be taken off study. A bone marrow biopsy will be done to assess response to the therapy up to that point or to determine etiology for inadequate recovery of counts.

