5	5/19/14	Study synopsis, section 4.2 - expand eligibility to include previously treated patients with refractory disease; Section 4.10 – delete prior therapy exclusion criteria – no longer applicable; Synopsis, sections 3, 7 - delete bone marrow biopsy between course 1 and 2 to minimize procedures but add off study marrow if patient discontinues treatment before completing two courses; Section 7.3 – delete the sentence “Final product must contain at least 30% NK cells.” as this is no longer correct based on the current CMC; Section 7.4 – update language to reflect current lot release criteria of > 3-fold NK cell enrichment between apheresis and final product; section 7.10 – redefine the definition of rapidly progressing disease based on peripheral blood since BM examination will not be routinely done between courses 1 and 2; section 10.2.9 – add that Vorinostat may be paid for by research funds; other edits and clarifications – all tracked	yes

Revision #	Version Date	Revision summary	Consent Revised
6	09/05/14	
Study synopsis, section 4.1, checklist - expand eligibility to include the following classifications of MDS:
 
 • International Prognostic Scoring System- Revised (IPSS-R) Category: High or Very High (Score of 5 or above) • WHO Classification: CMML that is not highly proliferative. WBC < 15k • Therapy related MDS • Severe cytopenias: Severe neutropenia (ANC \leq 0.8), platelet or PRBC transfusion dependent 
Update appendices IV (IPSS) to include IPSS-R
 
Section 7.6 and section 8.1 – add a bone marrow biopsy between course 1 and 2 for patients who failed prior treatment (prior to revision #5 all patients had a bm bx mid-treatment, with this revision it is reinstated for a sub-set of patients)
 
other edits and clarifications – all tracked
	yes
7	10/28/14	
Section 6 – clarify study enrollment/registration is on-study
 
Section 8 – increase the window that pre-treatment evaluations may be done (28 days unless otherwise stated, but 14 days for CBC, plt, CMP, chemistries), previously had been 14 days unless otherwise stated – clarify window is from start of treatment not study enrollment
 
Section 11.4 – update event reporting to IRB to new requirements (UMN only)
	no

INDEX

Contact Information – Key Study Personnel	2
Study Synopsis	7
Study Schema	8
1.0 Objectives.....	9
1.1 Primary Objective	9
1.2 Secondary Objectives	9
1.3 Correlative Laboratory Objectives.....	9

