7.10 Duration of Therapy

Patients will receive two courses of study treatment unless one or more of the following occurs:

- Patient withdraws consent or is non-compliant
- Criteria in section 7.6 for a 2nd treatment course are not met
- Medically unsafe, in the opinion of the treating investigator to continue with the treatment plan and based on development of grade 4 non-hematologic toxicities

- Intercurrent illness that prevents further administration of treatment
- Unacceptable toxicity
- Evidence of rapid disease progression defined as $\geq 20\%$ peripheral blood blast percentage suggesting progression to acute leukemia

Any patient who discontinues therapy before the completion of 2 courses should have a bone marrow biopsy and aspirate performed at the time treatment is discontinued. Those who are not evaluable per section 13 will be followed only until the resolution or stabilization of treatment related toxicity. No further follow-up for this study will be required, other than recording the date and cause of death upon knowledge in OnCore.

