8.1 Patient

8.1.1 Standard of Care and Investigational Treatment

	Pre-Treatment (within 28 days of treatment start)*	During each treatment course					4-6 weeks after 2 nd treatment course	Follow-up at Day 90, 180, 270, 360	
		Day 1 ¹	Day 5	Day 15 or 17	During IL-2 administration (Day 17-22)	Day 24, 31, 38, 45			
EVALUATIONS									
Written consent	X								
Medical history	X								
Disease Characteristics	X								
Pathology review of outside dx	X								
Transfusion History	X						X		
Concomitant meds	X	X					X		
Physical exam	X	X	X ⁶	X ⁶	X ⁶	X ⁶	X		
Vital signs	X	X		X					
Weight	X	X		X	3 x a week during IL-2	X			
Height	X								
ECOG Performance Status	X	X					X		
Survival Status								X ⁷	
LABORATORY									
CBC w/ diff ²	X	X	X	X	daily during IL-2	X	X		
Na, K, Cl, CO ₂ , BUN, creatinine, uric acid, phos, LDH, Mg	X	X	X	X		X			
ALT/AST, bili, total protein, albumin, alk phos	X	X		X		X			
Chest X-ray	X								
INR/PTT	X								
Pregnancy test ³	X								
HLA typing (low resolution)*	X								
Recipient Viral Serology	X								
ECHO/MUGA*	X								
Bone Marrow Bx/Asp ⁴	X ⁴					X ⁵	X ⁴		
Investigational TREATMENT									
Decitabine IV		Day 1-5							
Vorinostat PO			Day 6-15						
NK cell infusion (research)				Day 17					
IL-2 tiw for 3 doses (research)					X (start Day 17)				

* CBC, dff, CMP, chemistries within 14 days of study treatment start, HLA typing may be done at any time

- 1- Course 1 Day 1 evaluations need not be repeated if pre-study evaluations were done within 14 days of 1st treatment
- 2- CBC with diff weekly throughout all treatment with increased frequency as clinically indicated
- 3- Women of childbearing potential only; serum or urine
- 4- Bone marrow aspirate and biopsy with standard flow cytometry, conventional cytogenetics, and MDS/AML FISH panel will be conducted at study initiation and at the completion of the 2nd cycle for standard disease assessment or at time of study withdrawal if early termination.
- 5- Prior to course 2 ONLY in patients who enrolled in this study as a prior treatment failure per section 4.2.2 or any patient who is discontinuing study treatment after 1 course
- 6- Clinical assessments will occur at a minimum of weekly up until the NK cell infusion on Day +17 after which clinical assessments will occur daily until the day after the final IL-2 administration.
- 7- By record review, patient contact, etc.

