9.0 Study Endpoints

This study is designed as a two stage study of the combination of Decitabine and Vorinostat and haploidentical NK cell infusion. The primary endpoint is clinical response (CR + PR + HI) at the end of the required 2 cycles of therapy. An assessment of response differences between untreated/minimally treated and those with prior treatment failures will be conducted.

The secondary endpoints include evaluation of safety tolerability, the proportion of patients who become transfusion independent, the association of the in vivo NK cell expansion with clinical response, and 1 year Overall Survival.

Clinical responses are defined in Appendix VI.

Determination of toxicities will be important for this new combination. As per NCI CTCAE Version 4.0, the term toxicity is defined as adverse events that are classified as either possibly, probably, or definitely related to study treatment. The maximum grade for each type of toxicity will be recorded for each patient, and frequency tables will be reviewed to determine toxicity patterns. In addition, we will review all adverse event data that is graded as 3, 4, or 5 and classified as either “unrelated or unlikely to be related” to study treatment in the event of an actual relationship developing.

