Appendix VI – MDS Response Criteria

Based on International Working Group 2006 Modified Criteria

- Complete Remission (CR): $< 5\%$ myeloblasts with normal maturation of all cell lines
 - Persistent dysplasia will be noted
 - Peripheral Blood:
 - Hgb $\geq 11\text{g/dl}$
 - Platelets $\geq 100 \times 10^9/\text{L}$
 - Neutrophils ≥ 1000
 - Blasts = 0%
- Partial Remission (PR): all CR criteria if abnormal before except:
 - BM blasts decreased by $\geq 50\%$ over pre-treatment but still $>5\%$
- Marrow CR: Bone marrow with $\leq 5\%$ myeloblasts and decrease by $\geq 50\%$ over pretreatment with incomplete peripheral blood count normalization
- Hematologic Improvement (HI):
 - Hgb: Increase by $\geq 1.5\text{g/dl}$ or decreased PRBC transfusions by at least 4/8 week period (only PRBC given for Hgb $<9.0\text{g/dl}$)
 - Platelet Response: Absolute increase of $\geq 30 \times 10^9/\text{L}$ for those starting at $>20 \times 10^9/\text{L}$ For those $< 20 \times 10^9/\text{L}$ at baseline increase by 100% .
 - Neutrophil Response: at least 100% increase and an absolute increase of $>0.5 \times 10^9/\text{L}$
- Stable Disease: Failure to achieve at least a PR but no evidence of disease progression for >8 weeks
- Failure: Death during treatment or disease progression characterized by worsening cytopenias, increase percentage of marrow blasts, or progression to a more advanced MDS FAB subtype
- Cytogenetic Response:
 - Complete: Disappearance of any pre-treatment chromosomal abnormalities without the appearance of new ones
 - Partial: At least 50% reduction of chromosomal abnormality
- Disease Progression: Compared to pre-treatment values
 - Less than 5% blasts: greater than 50% increase to $>5\%$ blasts
 - $5\text{-}10\%$ blasts: greater than 50% increase to $>10\%$ blasts
 - $10\text{-}20\%$ blasts: greater than 50% increase to $>20\%$ blasts

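### Section 7.6 says delay where 7.10 says stop for rapid progression, the pre-course-2 marrow feeds no decision, and a patient stopped for progression is replaced instead of counted as a failure

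*Combined protocol and SAP*

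**What the plan says.** **Starting course 2.** Section 7.6 sets four conditions: neutrophil recovery to baseline, platelet support that is manageable for an outpatient, treatment-related non-hematologic toxicity down to grade 2 or lower, and no rapid progression in the sense of 7.10. It continues: "If the above requirements are not met, delay and reassess weekly until recovery occurs". Its off-study sentence applies after more than two weekly delays and names only hematologic recovery and toxicity.

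**Ending treatment.** Section 7.10 opens with "Patients will receive two courses of study treatment unless one or more of the following occurs". The list includes rapid progression and, as a separate item, unmet 7.6 criteria. It has no delay step. Rapid progression is a value of 20% or more for "peripheral blood blast percentage suggesting progression to acute leukemia". The study schema likewise makes the second course conditional on there being no rapid progression.

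**The extra marrow.** Under 7.6, a patient who entered as a prior treatment failure (4.2.2) "will have a bone marrow biopsy and aspirate performed prior to the start of the 2nd treatment course". Footnote 5 to the calendar in 8.1.1 schedules it "Prior to course 2 ONLY in patients who enrolled in this study as a prior treatment failure per section 4.2.2", or when a patient stops after one course. Section 3.0 plans correlative work between the courses, and 8.1.2 takes a research sample at each marrow biopsy.

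**Counting.** Section 6.2 replaces any patient who starts treatment and is then discontinued, whatever the reason. Section 13.1 limits the response evaluation to patients who complete both courses. Appendix VI has a Failure category that covers "disease progression characterized by worsening cytopenias, increase percentage of marrow blasts". Section 9.0 adds: "An assessment of response differences between untreated/minimally treated and those with prior treatment failures will be conducted".

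**The concern.** There are two separate points, about two different patients.

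1. A patient who meets the 7.10 definition of rapid progression gets two instructions: delay under 7.6, no second course under 7.10. The choice affects the primary endpoint. A stopped patient is replaced and disappears from the response rate, although the trial's own response criteria call progression a failure.

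2. A prior-failure patient can show marrow progression by Appendix VI before course 2 while blood blasts stay below the 7.10 definition. No course-2 rule uses that result. An investigator who sees it may stop treatment anyway, and the patient is then replaced. No such marrow is scheduled for untreated or minimally treated patients who are continuing, so stopping on it would change the denominator in one arm of the section 9 comparison only.

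**Working it through.** **Step 1: the passages side by side.**

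| Patient | 7.6 | 7.10 and schema | Response analysis (6.2, 13.1) |
|---|---|---|---|
| A: blood blasts 20% or more | Delay, reassess weekly; off-study sentence does not name progression | Second course not given | If stopped: replaced. If delayed and later given course 2 (only if blasts fall below 20%): stays in the denominator once both courses are completed |
| B: marrow blasts 12% to 25%, blood blasts below 20%, counts and toxicity acceptable | All four criteria met; course 2 proceeds | No listed progression event | Stays in the denominator on completing both courses. If stopped anyway: replaced |

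The marrow values for patient B are illustrative. They meet Appendix VI progression for a 10-20% baseline, which requires an increase of more than 50% to above 20%: 25/12 = 2.08, an increase of 108%, ending above 20%.

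**Step 2: reproduce the design.** Inputs from 13.1: 15 patients in stage 1, stop at 5 or fewer responses; 31 more, 46 in total; not worthy of further study at 18 or fewer; null 0.30, alternative 0.50.

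P(success) = sum over x = 6 to 15 of P(X1 = x) × P(X2 ≥ 19 − x), with X1 ~ Bin(15, p) and X2 ~ Bin(31, p).

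- p = 0.30: 0.0499 (plan: 5%)
- p = 0.50: 0.8032 (plan: 80%)

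The design is correct as stated.

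**Step 3: effect of stop-and-replace on the primary test.** Let d be the share of treated patients stopped for progression and replaced, all of them non-responders. A true rate p among all treated patients then becomes q = p/(1 − d) among evaluable patients. The documents do not give d; their only related figure is 10% dropout for all reasons. With p = 0.30:

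| d (assumed) | q | P(success) |
|---|---|---|
| 0 | 0.300 | 5.0% |
| 5% | 0.316 | 7.8% |
| 10% | 0.333 | 12.0% |
| 15% | 0.353 | 18.2% |
| 20% | 0.375 | 26.9% |

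If the same patients stay in the denominator as failures, P(success) remains 5.0% whatever d is.

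**Step 4: effect of the one-sided marrow on the section 9 comparison.** Assume a true response rate of 20% among prior-failure patients who start, and let m be the share of them stopped on the marrow and replaced. The observed rate is 0.20/(1 − m):

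- m = 0: 20.0%
- m = 5%: 0.20/0.95 = 21.1%
- m = 10%: 0.20/0.90 = 22.2%

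There is no matching change in the other group.

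**The case against.** **The delay sentence was written for counts and toxicity.** Its reference to recovery, and an off-study sentence confined to counts and toxicity, both suggest this. Section 7.10 and the schema supply the exit for progression. This is probably right about intent. The literal text still applies the delay to all four conditions, and 7.10 lists unmet 7.6 criteria as ending therapy without allowing any delay, so sites can differ.

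**Not tying course 2 to the marrow may be deliberate.** Section 2.3 argues that more than one cycle is needed to see consistent responses. Revision 5 moved to blood ("redefine the definition of rapidly progressing disease based on peripheral blood since BM examination will not be routinely done between courses 1 and 2"), and revision 6 brought the marrow back for prior failures. A reader might infer that 7.10 was overlooked, but the log does not show whether leaving it alone was accident or choice. The request is therefore to state the marrow's role, not to add a marrow criterion.

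**Three stronger readings are not supported.**

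- A reader might infer that one and the same progressing patient could be treated, delayed or stopped. Patient B is treated under the text; patient A is delayed or stopped, and neither section permits course 2 while blood blasts remain at 20% or more.
- A reader might infer that the biopsy has no use. It has a correlative use (3.0, 8.1.2); what is missing is a decision use.
- A reader might infer a large distortion of the group comparison, such as 20% becoming 33%. That needs 40% of prior-failure starters to be stopped on the marrow and replaced (0.20/0.60), against the protocol's own rules. The plan allows 10% dropout in total. Followed literally, it stops no one on the marrow and this bias is zero.

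**The inflation comes from the general replacement rule.** True: 6.2 and 13.1 affect every early stop, and 13.1 openly defines a completers' response rate. Progression nevertheless differs from other early stops, because Appendix VI already says how it is classified. The section 9 comparison also has no stated test or decision rule, which limits what hangs on it.

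**Conclusion.** The concern holds as two limited points. First, 7.6 and 7.10 give conflicting instructions for a patient with rapid progression by blood blasts, and the stop branch removes from the response rate a patient whose progression Appendix VI would class as failure. Second, the pre-course-2 marrow has no stated role in the decision on course 2. That leaves room for unplanned stopping, with replacement, in one group only.

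The sample size and error rates in 13.1 are not wrong. For the primary test, success would be declared 12.0% of the time instead of 5.0% if d is 10%. This assumes that the 30% null refers to all treated patients, that those stopped would not have responded, and that progression uses up the plan's whole dropout allowance; at d = 5% the figure is 7.8%. For the section 9 comparison the size is unknown: zero if nobody is stopped on the marrow, about two points in the prior-failure group if 10% are and the true rate is 20%, both assumed. The matter should be corrected, but it does not undermine the design.

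**What to change.** 1. Reconcile 7.6, 7.10 and Appendix VI so that they give one instruction for rapid progression. State which criteria the weekly-delay sentence covers, and whether the pre-course-2 marrow has any part in the decision. The sponsor should choose; no clinical rule or threshold is proposed here.
2. In 6.2 and 13.1, count any patient who started treatment and was stopped for disease progression, by blood or marrow, as a non-responder, and do not replace that patient.
3. Apply the same status in the section 9 comparison, so that each patient is counted one way throughout.

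The cost is a few sentences and no new procedure. The reported response rate may be slightly lower. Sections 7.10 and 7.11 tie the one-year follow-up to being evaluable, so the revision should also say whether these patients then enter that follow-up.

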6.2 Patients Who Do Not Begin Study Treatment

If a patient is registered on study, and is later found not able to begin the preparative regimen (beginning with the first dose of decitabine), for whatever reason, the patient will be removed from study and treated at the physician’s discretion. The patient will be considered a screen/baseline failure and the reason for removal from study will be clearly indicated in OnCore as detailed in the study’s Affiliate Manual. The patient will be replaced.

If a patient begins treatment, and then is discontinued for whatever reason, the patient will be replaced as the clinical response (CR + PR + HI) is not evaluable for response. If the patient discontinues therapy due to toxicity, it will count towards the toxicity stopping rules. The patient must be followed for any unresolved toxicity per section 7.10.

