11.2 Adverse Event Documentation

Adverse events occurring after the initiation of any study treatment must be documented. Adverse events attributed to a study-related procedure which occur prior to the initiation of study treatment must be documented as well. Refer to appendix VII for a list of expected toxicities.

For the purposes of this study, adverse event documentation requirements will be determined based on grade, expectedness and relationship to study therapy as follows:

	Grade 1	Grade 2		Grade 3		Grade 4 and 5
	Expected or Unexpected	Expected	Unexpected	Expected	Unexpected	Expected or Unexpected
Unrelated Unlikely	Not required	Not required	Not required	Not required	Required	Required
Possible Probable Definite	Not required	Not required	Required	Required non-hematological	Required	Required
				Not required - hematologic events		

All patients will be monitored from the initiation of any study treatment through day 45 after the last dose of study treatment or the start of a new treatment, whichever occurs earlier, as it is expected that most treatment related adverse events will occur during this period. However, the investigator is obligated, upon knowledge of, to report any adverse event considered to be related to study treatment meeting the expedited reporting criteria in section 11.4.

In addition, adverse event collection will include targeted adverse events and unexpected adverse events at specific time points in relation to the NK cell infusion and post NK cell infusion IL-2 injections.

Targeted adverse events (Appendix IX) and unexpected events will be collected at the following time points. Adjust the day to match the time point description. All time points are 24 hours +/- 2 hours.

- Post-Chemo/Pre-NK cell infusion (day 17)
- A single assessment 1-2 hours post NK cell infusion/pre IL-2 injection (day 17)
- pre IL-2 dose 2
- pre IL-2 dose 3
- 48 hours post IL-2 dose 3 (or to coincide with day 24 clinic visit)
- 1 week after last IL-2 dose (or to coincide with day 31 clinic visit)

At each time point, the worst grade of the targeted toxicity since the last assessment or the previous 24 hours (whichever is shorter) will be recorded in addition to any unexpected toxicities felt at least possibly related to the NK cells and/or the IL-2.

In addition, although not always a reportable event, deaths will be recorded in OnCore upon knowledge in the follow-up tab.

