11.3 Required Reporting: Mayo Clinic to the Masonic Cancer Center

Serious events: Beginning with the first dose of decitabine and continue through day 45 of the last treatment course, as an affiliate, Mayo will report all events meeting the definition of serious, regardless of attribution or expectedness, within 24 hours of knowledge of the event. After day 45 of the last treatment course, the investigator must report upon knowledge any event that is serious, unexpected and felt to be at least possibly related to study therapy.

Reports are to be submitted to the Study Coordinator at the University of Minnesota Masonic Cancer Center (MCC) using the SAE reporting form found in OnCore. The MCC Study Coordinator will facilitate reporting to the University Of Minnesota IRB and the FDA as required.

Stopping rule events: Any grade 4 or 5 non-hematologic, non-infectious toxicity occurring through day 45 of the last treatment course will count toward the early study stopping rule per section 13 and must be reported to the MCC Study Coordinator using the Early Stopping Rule Report Form found OnCore under the reports tab.

No more than one excess toxicity event will be accumulated per patient within in the same episode of toxicity (i.e. a grade 4 event worsening to a grade 5 is a single event) or when multiple events occur concurrently.

Events that count toward an early stopping rule do not necessarily constitute a serious adverse event requiring expedited reporting and

should be reported as such only if they meet the criteria for expedited reporting as defined in section 11.1.

Lot release issues: Any safety issues associated with the final lot release at the treating institution must be reported immediately to either [name] or [name] at the University of Minnesota (contact information on page 2) with follow-up reporting to MCC Study Coordinator using the Deviation Report found in OnCore.

Affiliate institutions will be responsible for submitting reportable events to their institutional IRB and any other required local regulatory entities.

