13.2 Early Stopping Rule for Toxicities

The complications and adverse events will be closely monitored in this study. The hypothesized rate of having grade 4 or 5 non-hematologic, non-infectious toxicities for the approach is 5%. Enrollment will be stopped and the trial re-evaluated if the grade 4 or 5 toxicity rate shows signs to exceed 15%. This means enrollment will be stopped and the study re-evaluated if there are 3 patients with a non-hematologic, non-infectious grade 4-5 toxic event occurring through day 45 of the last treatment course out of the first 7 patients, 4 out of 18, 5 out of 29, 6 out of 40, and 7 patients at any time. Toxicities such as infections, including but not limited to pneumonia, bacteremia, cellulitis, and neutropenic fever, etc are known results of high risk MDS and will not be included as toxicities attributed to the study therapy. Assessment for toxicities will begin upon initiation of trial therapy and will conclude 2 weeks after last dose of study related treatment. These stopping rules of a statistical sequential probability ratio test designed for no more than 5% the probability of type I error and at least 80% statistical power.

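### A grade 4-5 event on days 46-57 after course 1 counts toward the toxicity stopping rule if course 2 follows, but may not count if course 2 is cancelled for a reason other than toxicity

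*Combined protocol and SAP*

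**What the plan says.** **Waiting for course 2.** Section 7.6 states: "A second treatment course will be given 6 to 8 weeks after the start of course 1". Patients who do not meet the criteria are reassessed weekly. Removal follows under the condition "If more than 2 weekly delays occur (>8 weeks from the start of course 1") when counts or treatment-related toxicity have not recovered.

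**Counting window.** Section 13.2 applies the boundary to patients with a "non-hematologic, non-infectious grade 4-5 toxic event occurring through day 45 of the last treatment course". Section 11.3 repeats this for the affiliate site: such a "toxicity occurring through day 45 of the last treatment course will count toward the early study stopping rule per section 13". The reporting period in 11.4 ends on the same day. Section 13.2 also gives a second, shorter end of toxicity assessment, two weeks after the last study dose.

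**Discontinuation.** For patients who began treatment, section 6.2 says: "If the patient discontinues therapy due to toxicity, it will count towards the toxicity stopping rules". It names no grade and no time limit.

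**Documentation.** Section 11.2 records adverse events "through day 45 after the last dose of study treatment", or until a new treatment starts if that is earlier.

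**The concern.** Whether course 1 is the last course is not known while the patient is waiting. Take a grade 4 event on day 50 of course 1. If the patient recovers and starts course 2, the counting window has moved to day 45 of course 2 and the event is inside it. If course 2 never starts, the window closed on day 45 of course 1 and, under 13.2 and 11.3 alone, the same event is outside it. Counting thus depends on what happens after the event, and a site cannot settle it on the day.

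At stake is the boundary that protects patients enrolled later. Any event lost this way lowers the counted rate and never raises it. The affiliate's duty to report every serious event within 24 hours uses the same day-45 cut-off. After that day only serious, unexpected and possibly related events are due.

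**Working it through.** **1. Calendar.** Day 1 is the first decitabine dose. The last scheduled dose of a course is IL-2 on day 22 (7.5).

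- Six weeks from the start: 1 + 42 = day 43. Eight weeks: 1 + 56 = day 57.
- Two weeks after the last dose (13.2, second end date): 22 + 14 = day 36.
- Day-45 cut-off (13.2, 11.3, 11.4): day 45 of course 1 if it is the only course.
- 45 days after the last dose (11.2): 22 + 45 = day 67.

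The interval at issue is days 46-57, which is 12 days. Neither end date in 13.2 reaches it, so choosing between those two would not close it. The 11.2 window does reach it.

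**2. How a grade 4-5 event on days 46-57 is treated**

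| What follows the event | 13.2 / 11.3 (day 45) | 6.2 | 11.2 |
|---|---|---|---|
| Course 2 starts | Counted | Not needed | Documented |
| Course 2 cancelled because of the event | Not counted | Plausibly counted | Documented |
| Course 2 cancelled for counts, progression or withdrawal | Not counted | Not counted | Documented |

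The third row is the clear gap.

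**3. Reproducing the plan's boundary.** Inputs from 13.2: p0 = 0.05, p1 = 0.15, alpha = 0.05, power = 0.80. The upper line of the sequential probability ratio test is k = h + s·n, with D = ln[p1(1−p0)/(p0(1−p1))], s = ln[(1−p0)/(1−p1)]/D = 0.0919 and h = ln[0.80/0.05]/D = 2.292. Solving n = (k − h)/s gives 7.70, 18.58, 29.46, 40.34 and 51.21 for k = 3 to 7. Rounded down, these are 7, 18, 29, 40 and 51. The printed 3/7, 4/18, 5/29 and 6/40 match, and a limit of 7 at any time fits the planned maximum of 51 patients.

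Exact recursion of that boundary over 51 patients gives a stopping probability of 0.031 at a true 5% rate and 0.714 at 15%. The 80% in 13.2 is the nominal value for an open-ended test, so 71.4% is the reference here.

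**4. Size of the loss.** Counted rate = 0.15 × (1 − d × f). Here d is the share of patients who never start course 2 and whose events on days 46-57 go uncounted, and f is the share of their events that fall on those days. This takes the same 15% event rate in those patients as in the rest. The documents give neither d nor f. The 10% for d borrows the plan's predicted dropout over two courses (13.1). Under a constant hazard over 57 days, f = 12/57 = 0.211.

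| d | f | Counted rate | P(stop), n = 51 |
|---|---|---|---|
| 0 | – | 0.1500 | 0.714 |
| 0.05 | 0.211 | 0.1484 | 0.7035 |
| 0.10 | 0.05 | 0.1492 | 0.709 |
| 0.10 | 0.211 | 0.1468 | 0.693 |
| 0.10 | 0.40 | 0.1440 | 0.674 |
| 0.30 | 0.211 | 0.1405 | 0.649 |

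The d = 0.10 rows give 6.2 no credit. The d = 0.05 row supposes that half of the 10% stop because of toxicity and are counted through 6.2. The d = 0.30 row is a sensitivity case well above the plan's dropout figure.

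**The case against.** The strongest reply is that 6.2 already deals with the important case. A patient whose toxicity ends therapy counts, and no day limit is attached. Unresolved treatment-related toxicity bars course 2 under 7.6, and grade 4 non-hematologic toxicity is listed in 7.10 as a basis for stopping. The events most likely to prevent course 2 are therefore the ones that 6.2 picks up. This largely stands. A reader might infer from 13.2 and 11.3 that every grade 4-5 event on days 46-57, including a toxic death, is lost whenever course 2 does not start. The documents do not support that, because 6.2 can reasonably be read to count such patients. A loss of stopping probability above ten points, which a reader could reach by letting everyone wait to day 57 and every event block course 2, fails for the same reason. It also sits badly with a 10% predicted dropout.

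Two limits on the reply remain. Section 6.2 works only when toxicity is the reason for discontinuing, so it misses the third row of the table. It also has no stated route to the stopping-rule form: 11.3 asks the affiliate for events to day 45, and 11.4 refers to section 13.

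It is also fair to say that these events are not hidden from oversight. Section 11.2 documents them, related serious events stay reportable after day 45, and 13.1 includes all treated patients in the toxicity evaluation. The loss concerns the stopping-rule count, not the toxicity tables. A constant hazard may also overstate it, since days 46-57 lie 24 to 35 days after the last scheduled dose.

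**Conclusion.** The point holds in a narrow form. Sections 13.2 and 11.3, read as written, make counting depend on whether course 2 starts. Section 6.2 plausibly repairs this for events that end therapy. It leaves uncounted a grade 4-5 event on days 46-57 in a patient whose course 2 is cancelled for poor count recovery, progression or withdrawal.

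The effect is small and in one direction. At a true 15% rate the stopping probability falls from 71.4% to about 69-70%, a loss of one to two points. This assumes 10% non-starters, a constant hazard, the same event rate in non-starters, and either no credit or half credit for 6.2. Larger losses need a larger share of non-starters or later clustering of events than the documents indicate. The case for change rests on a safety boundary having one unambiguous window, not on the size of the loss.

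**What to change.** Reconcile 6.2, 11.2, 11.3, 11.4 and 13.2 to one stopping-rule window that depends neither on whether course 2 starts nor on when the patient is taken off study. The existing 11.2 documentation window would serve: from the first dose through day 45 after the last dose of study treatment, running without a break through the interval between courses. It reaches about day 67 when IL-2 ends on day 22, and it covers the wait to day 57 for any last dose on day 12 or later (12 + 45 = 57).

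Three details need wording:

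- Delete the sentence in 13.2 that ends assessment two weeks after the last dose.
- State that events counted through 6.2 fall under this window and go on the stopping-rule form.
- Say how the clause in 11.2 on starting a new treatment applies to the count, and that starting course 2 does not close the window.

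Extending the window only to the off-study date would be weaker. With a day 50 event, a patient removed on day 47 would go uncounted and one removed on day 57 would count.

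The cost is a few sentences. No visits are added, because 7.6 already reassesses weekly and 11.2 already documents these events. The downside is that a few more events count, so the boundary may be reached slightly sooner.
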